5.4.2 Secondary Analyses of Primary Outcome

The primary analysis of the primary outcome will be repeated using the ITT and per protocol populations as secondary analyses. Missing primary outcome data will need to be imputed for the ITT analyses; this will be done by assuming that these participants did not achieve $\geq 15\%$ weight loss at 52 weeks, which is a conservative approach.

5.4.3 Sensitivity Analyses

No sensitivity analyses are planned.

5.4.4 Exploratory Analyses

The per-protocol analysis of the primary outcome will be repeated in the per-protocol population but also excluding individuals had any of the following concomitant medications before their 52 week weight measure was recorded:

- Orlistat
- GLP-1 at glucose lowering dose
- Bupropion/Naltrexone
- SGLT-2 inhibitor which was started after randomisation

5.5 Secondary Outcome Analyses

5.5.1 Primary Analysis of Secondary Outcomes

Secondary anthropometric outcomes will be analysed in a similar way to the primary analysis. These outcomes will be summarised overall and by treatment group.

Categorial outcomes will be summarised using count and percentage. Continuous outcomes will be summarised using mean, standard deviation, median, range, and interquartile range. Binary anthropometric outcomes will be compared between the two treatment arms using logistic regression models with the anthropometric outcome as the outcome and randomisation group and the stratification factors (site, baseline BMI) as covariates. The adjusted odds ratio will be presented along with 95% confidence interval and p-value comparing the two treatment arms. Continuous anthropometric outcomes will be compared using linear regression models with the anthropometric outcome as the outcome and randomisation group and the stratification factors (site, BMI) as covariates. The adjusted mean difference will be estimated along with 95% confidence interval and p-value comparing the two treatment arms. If continuous outcomes are non-normally distributed then they will be transformed or a more suitable regression model will be selected.

No formal statistical testing will take place for the other secondary outcomes due to the large amount of secondary outcomes and to reduce multiple testing. Instead, descriptive analyses will be performed to explore potential patterns in improvements. This will apply to the outcomes relating to obesity-related co-morbidities, referrals to Tier 4 services, treatment satisfaction, treatment compliance, and physical activity. Categorial outcomes will be summarised using count and percentage. Continuous outcomes will be summarised using mean, standard deviation, median, range, and interquartile range. Where it makes sense to do so, for continuous variables the baseline, follow-up, and change values will all be summarised; some outcomes can only be defined at follow-up and so this will not apply to those outcomes.

In all analyses, participants will be analysed in the group to which they were randomised at baseline. Only the complete cases population will be used for the secondary outcomes to reduce the number of models being fitted. Participants who have undergone bariatric surgery during the period of the study will be excluded from these analyses if their bariatric surgery took place before the analysed time-point.

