8.3.1 Baseline Visit (Day 0) – All Participants

Only those patients who are eligible based on the data collected at the Screening and Consent Visit will proceed to the Baseline Visit (Day 0). Weight, waist circumference, blood pressure and pulse rate will be recorded for all the patients in line with study SOPs. The patient will also complete questionnaires to provide demographic and medical history details and additional data will be collected as indicated in Appendix 3 (e.g. self-reported physical activity using the International Physical Activity Questionnaire). Serious Adverse Event (SAE) and Adverse Event (AE) recording and documentation of changes in medication or diseases will be performed. Randomisation will be

performed and participants will be informed of their group allocation (see Randomisation Section 8.3.1.1 below). Participants in both groups (standard care [control group] vs. standard care + LIRA 3mg [targeted prescribing pathway]) will be counselled about the study visits and what they can realistically expect with each treatment option. Participants allocated to the targeted prescribing pathway will receive injection training, storage and dispensing. All participants will be informed that they may contact their GP or the study team at any time.

Urine pregnancy tests will be performed for females of childbearing potential. Additional testing will also occur at any time during the trial if a menstrual period is missed or as required by local law. The test will be performed at the study site. Pregnancy testing will not be required for women who have undergone a hysterectomy or bilateral tubal ligation, or for women above the age of 50 years old, who have been without menses for at least 1 year. Participants will be given clear instructions regarding contraception throughout the study. Adequate contraceptive measures have been defined as sterilisation, intra-uterine device, oral contraceptives, consistent use of barrier methods, male sterilisation or true abstinence (when this is in line with the preferred and usual lifestyle of the participant) (www.hma.eu/fileadmin/dateien/Human_Medicines/01-About_HMA/Working_Groups/CTFG/2014_09_HMA_CTFG_Contraception.pdf – accessed 21/07/2017).

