2.2 Secondary Endpoints

2.2.1 Definition and Derivation of Secondary Endpoints

Endpoint	Time point (weeks)	Endpoint derivation
Anthropometric endpoint		
Absolute change in weight (kg) from baseline	16, 32, 52, 104	Follow-up weight – baseline weight
Relative change in weight (%) from baseline	16, 32, 52, 104	(Baseline weight – follow-up weight)/baseline weight * 100
Weight loss of $\geq 5\%$, $\geq 10\%$ and $\geq 15\%$	16, 32, 52, 104	Binary indicator of 1 if relative change in weight from baseline is $\geq 5\%$ loss (or $\geq 10\%$ or $\geq 15\%$, respectively), 0 otherwise
Maintenance of weight loss of $\geq 15\%$ among those who lost $\geq 15\%$ at 52 weeks	104	Binary indicator of 1 if relative change in weight from baseline is $\geq 15\%$ loss, 0 otherwise, only calculated for those who lost $\geq 15\%$ of baseline weight at 52 weeks.
Absolute change in BMI (kg/m^2) from baseline	52, 104	Follow-up BMI – baseline BMI
Absolute change in waist circumference (cm) from baseline	52, 104	Follow-up waist circumference – baseline waist circumference
Obesity-related co-morbidities and their treatments (General)		
Score on King's College Obesity Staging System assessment	52, 104	Scored as per Staging System (Appendix 1) as Stage 0 (normal health), 1 (at risk of disease), 2 (established disease), 3 (advanced disease) with baseline values also presented
Quality of life (EQ5D) – Descriptive System	52, 104	Scored as per https://www.unmc.edu/centric/_documents/EQ-5D-5L.pdf with change from baseline value analysed separately for each dimension
Quality of life (EQ5D) – Visual Analogue Scale	52, 104	Scored as per https://www.unmc.edu/centric/_documents/EQ-5D-5L.pdf with change from baseline value analysed
Impact of Weight on Quality of Life-Lite (IWQOL-Lite)	52, 104	Transformed total score on scale of 0-100 scored as per https://www.qualityoflifeconsulting.com/iwgol-lite.html with change from baseline

		value analysed
Patient Health Questionnaire-9 (PHQ-9)	52, 104	Scored as per Appendix 2 as minimal depression, mild depression, moderate depression, moderately severe depression, severe depression with baseline values also presented
Patient Health Questionnaire-9 (PHQ-9)	52, 104	Total score generated as per Appendix 2 with change from baseline analysed
Obesity-related co-morbidities and their treatments (Obstructive Sleep Apnoea; OSA)		

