4.2 Missing Data

Attempts will be made to assess the primary outcome on all participants including those who have withdrawn from treatment. The number of missing observations for each outcome will be reported. If missing outcome data are present then the initial analysis will be based on the complete cases. A sensitivity analysis will then be carried out repeating the analyses with the ITT population to assess the possible impact of the missing data on the results produced. Missing primary outcome data will need to be imputed for the ITT analyses; this will be done by assuming that these participants did not achieve $\geq 15\%$ weight loss at 52 weeks, which is a conservative approach. We will also attempt to address bias by comparing the characteristics of those with missing outcome data to those who have completed follow-up. This strategy for dealing with missing outcome data has been recommended by White et al. (White 2011)

There should be no missing covariate data because site and baseline BMI are used as part of the randomisation process. The other covariate is treatment group which was assigned as part of the randomisation process and will be known for all participants.

Where participants were lost to follow up or missed a study visit, the study team attempted to access primary outcome data from existing hospital, GP or health records, where appropriate consent was in place.

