4.3 Derived/ Computed Variables

Analyses will be adjusted for the stratification variables which are study site and body mass index (BMI).

Study site is a non-ordinal, categorical, dummy variable with a unique code for each site.

BMI is a continuous variable calculated as weight in kg divided by height in metres squared. For stratification purposes, baseline BMI was dichotomised based on cut-off values of $\geq 45\text{kg}/\text{m}^2$ and $< 45\text{kg}/\text{m}^2$. This dichotomised grouping will be included in statistical models.

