5.5.3 Sensitivity Analyses

No sensitivity analyses are planned.

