5.8 Changes to the Planned Analysis

In the protocol, it stated that most secondary outcomes would be subject to formal statistical testing, with some secondary outcomes (safety, treatment compliance, treatment satisfaction) tabulated only, without statistical testing. However, due to the large number of secondary outcomes, it was decided that more secondary outcomes should be tabulated only to reduce the impact of multiple testing. The following outcomes were the ones for which the approach changed: obesity-related comorbidities, referrals to Tier 4 services, and physical activity.

In the protocol, the majority of the secondary outcomes were listed as absolute values, however the change from baseline will instead be analysed for continuous variables.

In the protocol, it states that ACR will be analysed as a secondary outcome for participants with diabetes. However, ACR was also measured for participants with prediabetes or hypertension and so these have been added to the ACR secondary outcome definition.

In the protocol, it was stated that participants who had bariatric surgery would be excluded from the complete cases, per protocol, and responder populations. However, it is more likely that these individuals will be poor responders and so excluding them could potentially bias the analyses. Therefore, participants who had bariatric surgery during the study period will be only be included at time-points prior to their bariatric surgery. They will be excluded from time-points after their bariatric surgery.

In the protocol, it stated that adjusted proportions or means would be presented by treatment group in the primary and secondary analyses. However, the unadjusted raw values are presented instead.

6 Safety and Adverse events (AEs)

The safety outcomes (including AEs and SAEs) will be summarised overall, by randomisation group, and by whether or not the participant was currently receiving LIRA 3mg treatment using count and percentage. The following information will also be presented:

- Incidence rate (per person-year) of each System Organ Class of AEs by treatment and overall
- Proportion of participants with at least one AE, by System Organ Class type, treatment arm, and overall
- Incidence rate (per person-year) of each expected AE type by treatment and overall
- Proportion of participants with at least one expected AE, by AE type, treatment arm, and overall
- Bar chart of number of AEs per individual, split by treatment

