Absolute waist circumference (cm) at 52 weeks								
Number								
Mean								
SD								
Median								
Range								
Interquartile range								
Absolute change in waist circumference (cm) at 104 weeks								

Outcome	Baseline		Follow-up		Change from baseline		Difference in change from baseline Adjusted mean difference (95% CI) ^a	P-value
	Control	Intervention	Control	Intervention	Control	Intervention		
Number								
Mean							-	-
SD							-	-
Median							-	-
Range							-	-
Interquartile range							-	-

Abbreviations: BMI, Body Mass Index; CI, Confidence Interval; OR, Odds Ratio.

^a Estimates are adjusted for the stratification variables: site and baseline body mass index ($\geq 45\text{kg}/\text{m}^2$; $<45\text{kg}/\text{m}^2$).

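### The models for change in weight, BMI and waist leave out the continuous baseline value of the outcome; adding it costs almost nothing and gains a little precision, probably mainly for waist

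*SAP*

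**What the plan says.** SAP 5.5.1 sets the model: "Continuous anthropometric outcomes will be compared using linear regression models with the anthropometric outcome as the outcome and randomisation group and the stratification factors", with site and BMI named in brackets as those factors. SAP 4.3 first describes BMI as continuous but then settles how it enters: "This dichotomised grouping will be included in statistical models", meaning at least 45 against below 45 kg/m². The footnote to Table 16.9 agrees: "Estimates are adjusted for the stratification variables: site and baseline body mass index", with the same cut-off. SAP 4.2, after naming site and baseline BMI, closes the list: "The other covariate is treatment group which was assigned as part of the randomisation process".

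The outcomes are change scores. SAP 5.8 says "the change from baseline will instead be analysed for continuous variables", and the endpoint table in SAP 2.2.1 defines each one as a change, for example "Absolute change in waist circumference (cm) from baseline". SAP 5.5.3 states "No sensitivity analyses are planned", so no alternative model brings the baseline value in.

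The baseline data exist. Protocol 8.3.1 says of Day 0: "Weight, waist circumference, blood pressure and pulse rate will be recorded for all the patients in line with study SOPs". BMI follows from the height measured at screening.

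**The concern.** A change score fixes the slope of follow-up on baseline at 1. If the true slope is b, a share (1 − b) of any chance difference between arms in baseline value within a BMI stratum stays in the estimated effect, and the matching part of the between-person variance stays in the residual. The BMI split removes only the part of baseline variation that lies between its two categories. That leaves a good deal of the variation in weight, and more of the variation in waist.

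The stake is precision in a few secondary comparisons. The continuous anthropometric outcomes are among the few secondary outcomes for which SAP 5.5.1 still plans confidence intervals and p-values. Bias is not at issue, because the planned estimate is unbiased over randomisation. The primary logistic model and the binary anthropometric models are not affected.

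**Working it through.** **Plan's own figures.** Neither document gives a sample size, SD or correlation for the continuous outcomes. The only stated figure is 392 (261 and 131) for the binary primary outcome: 5% against 16%, two-sided 5% alpha, 80% power, 2:1 allocation, 25% drop-out (Protocol 11.2). The pooled two-proportion formula gives 96 + 192 = 288, and 288/0.75 = 384. At 98 and 196 completers the power is 81.2%. So 392 is reproduced to within about 2%, and this point does not change it. The planned completers used below are 261 × 0.75 = 195.75 and 131 × 0.75 = 98.25, taken as 196 and 98.

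**Formula.** Scale the baseline SD to 1. Let ρ be the baseline to follow-up correlation, s the ratio of follow-up SD to baseline SD, b = ρs the slope, and R² the share of baseline variance explained by the BMI split. With baseline in the model the residual variance is s²(1 − ρ²). Without it, (1 − b)²(1 − R²) is added. Hence

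SE without / SE with = √[1 + (1 − b)²(1 − R²) / (s²(1 − ρ²))].

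**Assumed R².** A split with 30% or 40% of participants in the upper group has correlation 0.759 or 0.789 with the normal variable that it divides. The correlation with BMI is assumed to be 0.8 for weight and 0.7 for waist.
- BMI: 0.759² to 0.789² = 0.58 to 0.62
- Weight: 0.64 times that = 0.37 to 0.40
- Waist: 0.49 times that = 0.28 to 0.31

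**Results at equal SDs (s = 1), SE larger without baseline:**

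| Outcome | ρ = 0.8 | ρ = 0.9 |
|---|---|---|
| BMI | 2.1–2.3% | 1.0–1.1% |
| Weight (kg) | 3.3–3.4% | 1.6% |
| Waist | 3.8–3.9% | 1.8–1.9% |

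For example, waist at ρ = 0.8 and R² = 0.28: 0.04 × 0.72/0.36 = 0.080, and √1.080 = 1.039. Over ρ 0.8–0.95 and s 0.9–1.1 the range is 0 to 9.2%. The largest value is for waist at ρ = 0.7 and s = 0.9: b = 0.63, 0.37² × 0.72/(0.81 × 0.51) = 0.239, and √1.239 = 1.113, or 11.3%.

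**Simulation.** Six scenarios of 2,500 trials each, with 196 against 98 and five sites. Assumed inputs: mean BMI 42.4 (SD 5.8), 25% at or above 45, SD of % loss 7 or 9, waist SD 12 cm, waist measurement SD 3–5 cm. Model SE without baseline compared with SE with it:
- Waist: 0.7% to 3.7% larger
- Weight in kg: 0.1% to 0.3% larger
- BMI: −0.02% to +0.06%
- % change: 0.2% smaller, when % loss is unrelated to baseline weight

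Weight gains less here than in the table. If % loss does not depend on baseline weight, the slope is one minus the mean proportional loss, which is close to 1. If % change does correlate with baseline weight within strata, at 0.1 or 0.2, then 1/√(1 − r²) − 1 = 0.5% or 2.1%.

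**Read as a gain.** For waist at ρ = 0.8, equal SDs and 40% in the upper stratum, adding baseline lowers the SE by 3.7% by formula and 3.5% in a separate simulation. The variance falls by 7.2%, and 0.072 × 294 is about 21 participants. A comparison with 80% power would rise to about 82.8%.

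**Imbalance left in the estimate (waist, SD 12 cm).** One SE of chance imbalance within BMI strata is 12 × √(1 − R²) × √(1/98 + 1/196) = 1.24–1.26 cm. With slopes from 0.9 down to 0.7, 10–30% of it remains: 0.12–0.38 cm.

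**The case against.** The strongest reply is that the effect is too small to matter. Change scores adjusted for the stratification factors are valid, the covariates follow Protocol 11.1, and outside waist the simulated gain is close to nil. Table 16.9 also shows baseline values by arm, so a reader could see an imbalance. All of this is true. It limits the priority but does not remove the reason for a cheap change.

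Other points stand in part:
- **Cost.** Baseline weight makes the SE for % change 0.2% larger in the simulated case. That is roughly the price of one degree of freedom. The new covariate also departs from the protocol and should be recorded as such.
- **Responder analysis (SAP 5.5.2).** It repeats these models in groups that are no longer comparable by randomisation, so there the covariate can move the estimate as well as its SE. That analysis is non-randomised already, and the covariate does not make it worse.
- **Assumptions.** A larger gain for waist depends on waist having a lower slope than weight or BMI. With follow-up SD 5% below baseline SD, the SE for weight would also fall by about 3%.
- **Imbalance.** The wider SE already allows for chance imbalance on average, so the 0.12–0.38 cm illustrates the precision loss and is not a second harm.

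One objection fails. Working back from the simulated 0.7–3.7% to slopes of about 0.81–0.96 would put the remaining imbalance below the range given, but that step assumes equal SDs. A further waist simulation at 196 and 98 gave an SE 0.8–4.1% larger with slopes of about 0.76–0.88, so 12–24% remains, inside the 10–30% range.

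**Conclusion.** The point holds as an optional improvement. The omission is plain in SAP 4.2, 4.3, 5.5.1 and Table 16.9. The planned models are valid without the covariate, and no conclusion is shown to depend on it. The likely loss is a standard error 1–4% too large for waist and close to nil for weight in kg, BMI and % change. The formula reaches 9% over the main range of assumptions and 11% at the extreme. Every SD, correlation and stratum share is assumed, so the ordering of the outcomes is less certain than the conclusion that the gain is small.

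**What to change.** In SAP 5.5.1 and 4.3, state that each continuous anthropometric model also includes the continuous baseline value: baseline weight for change in kg and in %, baseline BMI for change in BMI, and baseline waist for change in waist. Keep site and the BMI stratum indicator in every model. Amend the Table 16.9 footnote to match, and record the addition in SAP 5.8. In SAP 5.5.2, say whether the responder models carry the same covariate.

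The cost is a few lines of text and one degree of freedom per model. Each change already needs its baseline value, so no further participant is excluded. The SAP copy is marked as a draft and is to be signed off before database lock. If lock has already taken place, which the documents do not show, report the adjusted models as an added analysis and label them so.

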1.2.3 Treatment groups

1.2.3.1 Intervention group (Targeted Prescribing Pathway)

The NHS Weight Management pathway is divided into four distinct tiers:

***Tier 1:** health promotion*

***Tier 2:** lifestyle interventions*

***Tier 3:** specialist multidisciplinary weight management services*

Tier 4: bariatric surgery

Across the UK, each region has a specialist Tier 3 obesity and/or weight management service or equivalent, usually referred to as Tier 3. This includes a clinician led multidisciplinary team approach, potentially including a specialist physician, nurse, dietician, psychologist, physiotherapist, etc. From this point forwards, Tier 3 specialist weight management and/or equivalent services will be referred to as 'Tier 3' throughout the remainder of this protocol.

Participants in the intervention group will receive the same standard care as those in the control group, i.e. the best medical practice delivered by the Tier 3 service at each site. Additionally, at baseline, LIRA 3mg will be prescribed to all of the participants in the intervention group at a starting dose of 0.6mg daily. Dose escalation of Liraglutide will occur according to a pre-specified titration protocol, from 0.6mg to a maximum of 3.0mg daily. Liraglutide dose will be initiated at 0.6mg and then increased to 1.2mg in Week 2, 1.8mg in Week 3, 2.4mg in Week 4, and 3.0mg in Week 5. Participants in the intervention group will be aware that the LIRA 3mg treatment may be stopped at various time points throughout the duration of the study and that continued use of LIRA 3mg is based upon their response to the treatment in terms of them achieving pre-defined weight loss targets at 16, 32 and 52 weeks. Specifically, participants in the intervention group will continue to be prescribed LIRA 3mg for the 104 week duration of the study, unless one of the following stopping rules applies:

1st stopping rule

After 16 weeks (\pm 14 days) on the medication, only those participants who have lost $\geq 5\%$ of their baseline weight will be offered further treatment with LIRA 3mg for another 16 weeks. Participants who have not met this weight loss target will have their LIRA 3mg treatment stopped but will still continue in the targeted prescribing pathway but will receive standard care only during the remainder of the study.

2nd stopping rule

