1.2.5 Randomisation and blinding

This is an open-label study and so there is no blinding.

Randomisation will be conducted through a validated online system (sealedenvelope.com) provided through the LCTU. Eligible participants will be randomly assigned at their Baseline Visit (Day 0) in a 2:1 ratio to participate in a Tier 3 service with:

- 1) *Targeted prescribing pathway - The use of once daily subcutaneous injections of Liraglutide (if they meet the pre-specified criteria), starting at a dose of 0.6 mg with gradual and pre-specified increments to 3.0mg*
or
- 2) *Control Group - No additional treatment.*

A 2:1 ratio will be used so that a sufficient number of responders will be available for responder analyses. Randomisation will be stratified by centre and BMI ($\geq 45\text{kg}/\text{m}^2$; $< 45\text{kg}/\text{m}^2$).

Participants will be informed of their randomisation assignment during the Baseline Visit. A letter will be sent to the participant's GP notifying them of their patient's participation in the study. Both the participant and their GP will have the randomisation assignment confirmed by letter.

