4.6 Statistical Significance

All statistical tests, p-values, and confidence intervals will be two-sided. Statistical significance will be assessed at the 5% level for main effects. No interaction analyses are planned, however if post-hoc interaction effects are tested then these will be assessed at the 10% level.

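### SAP 5.5.1 does not say how unequal variance between arms is handled for weight, BMI and waist change; with 2:1 allocation, robust standard errors are a cheap safeguard

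*SAP*

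**What the plan says.** SAP 5.5.1 sets the method: "Continuous anthropometric outcomes will be compared using linear regression models with the anthropometric outcome as the outcome". The covariates are randomised group, site and BMI. On reporting it says: "The adjusted mean difference will be estimated along with 95% confidence interval and p-value comparing the two treatment arms". The outcomes concerned are change in weight in kg and in per cent (weeks 16, 32, 52 and 104) and change in BMI and waist (weeks 52 and 104), as listed in SAP 2.2.1.

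The one provision for a failed assumption is: "If continuous outcomes are non-normally distributed then they will be transformed or a more suitable regression model will be selected". It is triggered by non-normality; unequal variance is not mentioned. SAP 5.5.3 adds: "No sensitivity analyses are planned". SAP 4.6 applies two-sided tests at the 5% level.

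Two design features bear on this. Allocation is unequal by intent (SAP 1.2.5): "A 2:1 ratio will be used so that a sufficient number of responders will be available for responder analyses". And the intervention is a pathway with weight-loss targets at weeks 16, 32 and 52 (SAP 1.2.3.1): "Participants who have not met this weight loss target will have their LIRA 3mg treatment stopped". Those participants stay in the intervention arm for analysis (SAP 4.1).

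Neither document gives an SD for any continuous outcome in either arm.

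**The concern.** Linear regression with default settings uses one residual variance for everybody. If the arms are of equal size, unequal spread hardly disturbs the standard error of the group difference. At 2:1 that protection is gone. If the larger arm is the more variable, the standard error is too large; if the smaller arm is, it is too small.

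This trial has a specific reason to expect unequal spread. After week 16 the drug continues only in those who are losing weight, so the intervention arm becomes a mix of people on and off treatment, and the control arm has no counterpart to that split. A more variable intervention arm, which is the larger arm, is therefore plausible. The consequence would be intervals somewhat too wide and some power lost on the continuous secondary outcomes that receive a formal test. Unequal variance can occur with perfectly normal data, so the non-normality clause need not catch it, and no sensitivity analysis would show it.

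**Working it through.** **Inputs from the documents.** 392 randomised (261 v 131), 25% drop-out, 5% v 16% reaching 15% loss, 80% power, two-sided 5% (SAP 1.2.4, 4.6; Protocol 11.2). **Assumed:** every SD, mean and mean difference below.

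**1. The plan's own figure.** The pooled two-proportion formula for 5% v 16% at 2:1 gives 96 + 192 = 288 evaluable, and 288/0.75 = 384, close to 392. With 0.75 × 131 ≈ 98 and 0.75 × 261 ≈ 196, power is 81%. The sample size is sound, and 98 v 196 is used from here on.

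**2. Error in the pooled standard error.** Let r be intervention SD / control SD and n the control arm size, with 2n in the intervention arm. In units of control variance/n, the pooled model variance is r² + 0.5 and the true variance is 1 + 0.5r². So

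k = model SE / true SE = √[(r² + 0.5)/(0.5r² + 1)],

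coverage = 2Φ(1.96k) − 1, and test size = 1 − coverage. With equal arms k = 1 for every r.

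**3. SD ratios under normal data and the plan's response rates.** Assume control mean loss 4%. Control SD = (15 − 4)/1.645 = 6.7. For mean difference d, intervention SD = (15 − 4 − d)/0.994. Power is by normal approximation.

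| d (points) | Intervention SD | r | k | Coverage | Power, pooled SE v true SE |
|---|---|---|---|---|---|
| 2 | 9.0 | 1.35 | 1.10 | 96.9% | 49% v 57% |
| 2.5 | 8.5 | 1.28 | 1.08 | 96.6% | 73% v 78% |
| 3 | 8.0 | 1.20 | 1.06 | 96.3% | 90% v 92% |
| 3.5 | 7.5 | 1.13 | 1.04 | 95.9% | 98% v 98% |

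In sample-size terms the loss is 1 − 1/k²: 18% at d = 2, falling to 8% at d = 3.5.

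The direction depends on the assumptions. Equal SDs require d = (15 − m)(1 − 0.994/1.645) for control mean m: about 5.1 points at m = 2%, 4.35 at 4%, 3.6 at 6%. Above that value r falls below 1.

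**4. A second model, closer to the pathway.** Suppose a fraction q of the intervention arm gains an extra loss D, the rest behave like controls, and the within-group SD is 6.69 throughout. D is chosen so that 16% of the arm reach 15% loss. Then intervention SD² = 6.69² + q(1 − q)D².

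| q | D | Intervention SD | r | k | Coverage |
|---|---|---|---|---|---|
| 0.2 | 12.69 | 8.40 | 1.26 | 1.08 | 96.5% |
| 0.4 | 7.97 | 7.74 | 1.16 | 1.05 | 96.0% |
| 0.6 | 6.13 | 7.33 | 1.10 | 1.03 | 95.7% |

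Control means of 3% and 5% give the same ratios.

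**5. The opposite direction.** At r = 0.8, k = √(1.14/1.32) = 0.93: the standard error is 7% too small and the test size is 6.9%.

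**6. Does the remedy work?** In 10,000 simulated trials per scenario (98 v 196, five sites, a BMI stratum, mixture data, no true difference), type I error was:

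| r | Ordinary SE | HC3 |
|---|---|---|
| 1.00 | 0.050 | 0.047 |
| 1.11 | 0.048 | 0.053 |
| 1.21 | 0.036 | 0.047 |
| 1.43 | 0.027 | 0.046 |

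**The case against.** A reader might infer that the planned intervals and p-values will be wrong. The documents do not support that. No SD is given, the SAP is silent on the estimator rather than committed to a pooled one, and SAP 4.5 leaves the software open. The 5% and 16% targets do not by themselves imply unequal variance: that needs an assumed distribution, control mean and mean difference. This objection stands.

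A reader might also infer inflated false positives. The mechanism in the pathway points the other way, to a conservative error. A ratio of 0.8 is arithmetically possible, but nothing in the documents gives a reason to expect it in the main analysis. That stands too.

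Three further limits hold. The first stopping rule acts only after the week-16 assessment, so there is no rule-based split in the week-16 outcomes. Controls may receive other anti-obesity drugs (SAP 1.2.3.2), which adds spread on their side. And the loss of power is noticeable only at small mean differences; at 3 points or more it is about 2 percentage points or less.

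Finally, a strongly split arm would look non-normal and might trigger the existing clause. That is a partial safeguard at most: the clause does not say which model would follow, a transformation need not equalise variances, and a moderate split could pass unnoticed.

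**Conclusion.** The gap is real but modest. SAP 5.5.1 leaves unequal variance unaddressed in a design whose allocation makes the default standard error sensitive to it. This is a cheap improvement to the plan, not an analysis that is wrong as written.

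For assumed SD ratios of about 1.1 to 1.35, the pooled standard error is about 3% to 10% too large and coverage about 95.7% to 97%. The largest loss of power in the range examined is 49% v 57%, at a 2-point difference. With equal SDs there is no loss, and with a less variable intervention arm the test would be mildly liberal. All of this rests on assumed SDs, means and response distributions. The adjusted mean difference is unaffected, as is the logistic primary analysis; only secondary outcomes are involved.

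**What to change.** In SAP 5.5.1, keep the linear model, its covariates and the adjusted mean difference. Add one sentence: 95% confidence intervals and p-values for the continuous anthropometric outcomes will use heteroscedasticity-robust (HC3) standard errors. Stating this before database lock also removes a later choice between standard errors.

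The cost is one sentence and one software option. Point estimates do not change, and if variances are in fact equal the loss of precision is negligible.

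SAP 5.5.2 repeats these models in the responder analysis, so it would be sensible for the sentence to carry over. There the size imbalance reverses: about 31 responders (261 × 0.75 × 0.16) against 98 controls after drop-out. The pooled standard error could then err in either direction: test size is 8.1% at an assumed SD ratio of 1.25 and 1.7% at 0.67.
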